## **CLINICAL TRIAL PROTOCOL SYNOPSIS**

Name of company: Boehringer Ingelheim	Tabulated Trial Protocol	
Name of finished product: Not applicable		
Name of active ingredient: BI 655130		
Protocol date: 08 March 2017	Trial number: 1368-0003	Revision date: Not applicable
Title of trial: Safety, tolerability, and pharmacokinetics of two dose strengths of a single subcutaneous dose of BI 655130 and one single intravenous dose of BI 655130 in healthy male and female subjects (open-label, parallel group design)		
Principal Investigator:		
Trial site:		
Clinical phase: I		
Objectives: To investigate safety, tolerability, and pharmacokinetics of two dose strengths of a single subcutaneous injection of BI 655130 and relative bioavailability of one strength of the subcutaneous formulation compared to an intravenous dose		
Methodology: Open-label, partially randomised design		
No. of subjects:  total entered: 36 each treatment: 12		
Diagnosis: Healthy subjects assigned to the intravenous dose will be matched for gender and body weight ( $\pm 10\%$ ) to subjects receiving the subcutaneous dose		
Main criteria for inclusion: Healthy male and female subjects, age of 18 to 50 years, body mass index (BMI) of 18.5 to 29.9 kg/m 		
Test product: BI 655130 solution for injection dose: and [Test] mode of admin.: Subcutaneous (SC) injection (perumbilical)		
Comparator product:  dose: mode of admin.: Intravenous (IV) as 30 min infusion		
Duration of treatment: One day (single dose) for each treatment		

Proprietary confidential information © 2017 Boehringer Ingelheim International GmbH or one or more of its affiliated companies

Name of company:		Tabulated Trial Protocol	
Boehringer Ingelheim			
Name of finished product:			
Not applicable			
Name of active ingredient:			
BI 655130			
Protocol date:	Trial number:		Revision date:
08 March 2017	1368-0003		Not applicable
Criteria for pharmacokinetics:	Primary endpoints: $AUC_{0-tz}$ and $C_{max}$ Secondary endpoints: $AUC_{0-\infty}$		
Criteria for safety:	Adverse events (AEs) including clinically relevant findings from the physical examination, local tolerability, safety laboratory tests, 12-lead electrocardiogram (ECG), continuous ECG monitoring, vital signs (blood pressure [BP], pulse rate [PR]) and oral body temperature		
Statistical methods:	Relative bioavailability will be estimated by the ratios of the geometric means (test/reference) for the primary and secondary endpoints. Additionally, their two-sided 90% confidence intervals (CIs) will be provided. This method corresponds to the two one-sided t-tests procedure, each at the 5% significance level. Since the main focus is on estimation and not testing, an acceptance range was not specified. The statistical model will be an ANOVA on the logarithmic scale including effects for 'treatment'. CIs will be calculated based on the residual error from ANOVA. Descriptive statistics will be calculated for all endpoints.		

Proprietary confidential information © 2017 Boehringer Ingelheim International GmbH or one or more of its affiliated companies

## FLOW CHART

Single dose of BI 655130 as SC, SC or single IV infusion of of BI 655130 (subjects will receive only one dose)

Visit	Day	Time relative to first drug administration (planned time [h:min])	Approx. time (actual time) [h:min]	Event and comment	PK plasma 	Laboratory/ Urinalysis 	Body Temperature	Body Weight	12-lead ECG	ECG monitoring	Vital signs (BP, PR)	Query on adverse events, concomitant therapies 
1	-28 to -3			screening 		X		X	X		X	
2	-2	-48:00	8:00	ambulatory visit		X 						
2	-1	-12:00	20:00	admission to trial site		X 						X
1	1	-2:00	6:30		X 	X 	X 		X 		X 	X 
		0:00	8:00	drug administration start of infusion or SC injection						▲		
		0:30	8:30	▼ end of infusion 	X		X	X	—		X	X 
		1:00	9:00								X	
		1:30	9:30						X		X	
		2:00	10:00	light breakfast 	X		X	X	▼		X	
		2:30	10:30									
		3:00	11:00		X						X	
		4:00	12:00	Lunch 	X	X 					X	X 
		6:00	14:00				X	X			X	
		8:00	16:00	snack (voluntary) 	X						X	
		10:00	18:00	Dinner 								
		12:00	20:00		X		X	X			X	X 
	2	24:00	8:00	Breakfast 	X	X 	X		X		X	X 
		28:00	12:00	Lunch 								
		32:00	16:00	snack (voluntary) 			X				X	
		34:00	18:00	Dinner 								X 
3	48:00	8:00		Breakfast  discharge from trial site (confirmation of fitness) 	X				X		X	X 
4	72:00	8:00		ambulatory visit	X		X					X 
5	96:00	8:00		ambulatory visit	X							X 
6	120:00	8:00		ambulatory visit	X							X 
7	144:00	8:00		ambulatory visit	X							X 
8	168:00	8:00		ambulatory visit	X		X		X		X	X 
15	336:00	8:00		ambulatory visit	X							X 

Proprietary confidential information © 2017 Boehringer Ingelheim International GmbH or one or more of its affiliated companies

Visit	Day	Time relative to first drug administration (planned time [h:min])	Approx. time (actual time) [h:min]	Event and comment	PK blood 	Laboratory/ Urinalysis 	Body Temperature	Body Weight	12-lead ECG	ECG monitoring	vital signs (BP, PR)	Query on adverse events, concomitant therapies 
2	22	504:00	8:00	ambulatory visit	X	X			X		X	X
	29	672:00	8:00	ambulatory visit	X	X			X		X	X 
	36	840:00	8:00	ambulatory visit	X							X
	43	1008:00	8:00	ambulatory visit	X							X
	57	1344:00	8:00	ambulatory visit	X							X 
	71	1680:00	8:00	ambulatory visit	X							X
	92 ±2	2184:00	8:00	ambulatory visit	X							X
	120 ±3	2856:00	8:00	ambulatory visit	X							X
	148 ±3	3528:00	8:00	ambulatory visit	X							
3	176 ±3	4200:00	8:00	EOT 	X 		X	X	X	X	X	X 

1. Screening with subject information, informed consent as the first measure, includes physical examination, check of vital signs, ECG, safety laboratory (under fasting conditions), pregnancy test, drug screening, demographics (including determination of body height and weight, smoking and alcohol history), relevant medical history, concomitant therapy and review of inclusion/exclusion criteria.
2. The time is approximate; procedures are to be performed and completed within 3 h prior to drug administration. Within 3 hours prior to the planned dosing, planned time -2:00 will be used.
3. Laboratory tests (safety laboratory) include clinical chemistry, haematology, coagulation and urinalysis; in addition at screening: serology (HBV, HCV, HIV), and drug screening.
4. PK sampling times may be adapted based on information obtained during trial conduct.
5. Standardized assessment of local tolerability only for subcutaneous injection using the criteria swelling, induration, heat, redness, pain or other findings.
6. If several actions are indicated at the same time point, the intake of meals will be the last action.
7. Confirmation of fitness includes physical examination.
9. At baseline, cytokine (IL1β, IL6, TNF-α and IFNγ) samples will be collected together with safety lab. Additional cytokine samples IL1β, IL6, TNF-α and IFNγ will be collected at 4 h and 24 h post-dose. Cytokine samples are only to be analysed from an individual subject in case of specific adverse events in this subject that are suggestive for a cytokine release. At 4 h and 24 h post-dose no safety lab needs to be taken.
10. Only drug screening and alcohol breath test.
11. AEs and concomitant therapies will be recorded throughout the trial, but will be specifically asked for at the time points indicated in the [Flow Chart](#) above.
12. EOT (End of trial examination) includes physical examination, body weight, vital signs, ECG, safety laboratory, recording of AEs and concomitant therapies. EOT to be performed not before last PK and ADA sampling.
13. Safety laboratory is to be taken within two days prior to study drug administration and can be omitted if the screening examination is performed between Day -5 and Day -3.
14. First measure after completion of infusion is the collection of PK sample
15. In case plasma levels still exceed LOQ additional PK samples may be collected beyond Day 176 ±3.

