### 5.2.2.2 Adverse event collection and reporting

#### AEs collection

Upon enrolment into a trial, the subject's baseline condition is assessed (for instance, by documentation of medical history/concomitant diagnoses), and relevant changes from baseline are noted subsequently.

[figure not shown]
Subjects will be required to report spontaneously any AEs as well as the time of onset, end, and intensity of these events. In addition, each subject will be regularly assessed by the medical staff throughout the clinical trial and whenever the investigator deems necessary. As a minimum, subjects will be questioned for AEs (and concomitant therapies) at the time points indicated in the [Flow Chart](#). Assessment will be made using non-specific questions such as 'How do you feel?'. Specific questions will be asked wherever necessary in order to more precisely describe an AE.

A careful written record of all AEs shall be kept by the investigator in charge of the trial. Records of AEs shall include data on the time of onset, end time, and intensity of the event as well as any treatment or action required for the event and its outcome.

The following must be collected and documented on the appropriate CRF(s) by the investigator:

- From signing the informed consent onwards until an individual subject's end of trial:
  - All AEs (serious and non-serious) and all AESIs
  - The only exception to this rule are AEs (serious and non-serious) and AESIs in Phase I trials in healthy volunteers, when subjects discontinue from the trial due to screening failures prior to administration of any trial medication. In these cases, the subjects' data must be collected at trial site but will not be entered in the CRF or trial database and will not be reported in the CTR
- After the individual subject's end of trial:
  - The investigator does not need to actively monitor the subject for AEs but should only report related SAEs and related AESIs of which the investigator may become aware of by any means of communication, e.g. phone call. Those AEs should, however, not be reported in the CRF.

Proprietary confidential information © 2017 Boehringer Ingelheim International GmbH or one or more of its affiliated companies

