The REP for BI 655130, when measurable drug levels or PD effects are still likely to be present after the last administration, is not known at this early stage of development. Therefore, all AEs reported until the end of trial examination will be considered on treatment; please see [Section 7.3.3](#).

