## **6. GENERAL ANALYSIS DEFINITIONS**

### **6.1 TREATMENTS**

For basic study information on treatments to be administered, assignments of dose groups, and selection of doses, cf. Section 4 of the CTP.

Subjects were planned to be treated either with one single dose of

- as subcutaneous (SC) injection (exploratory reference treatment (ER))  
or
- as intravenous (IV) infusion (reference treatment (R))  
or
- as SC injection (test treatment (T)).

For statistical analysis of AEs, safety laboratory data and vital signs, the following analysis phases are defined for each subject:

Table 6.1: 1 Flow chart of analysis phases for statistical analyses of AEs, safety laboratory data and vital signs

Study analysis phase	Label	Start (inclusive)	End (exclusive)
Screening	Screening	Date of informed consent	Date/time of administration of study drug
On-treatment	BI SC, or BI IV or BI SC, respectively	Date/time of administration of study drug	0:00 AM on day after subject's trial termination date

CTR Section 15, Appendix 16.1.9.2.8.2 and Appendix 16.1.9.2.8.3 AE displays will present results for the on-treatment phase only.

In CTR Section 15 AE tables (but not in Appendix 16.1.9.2.8.2 and Appendix 16.1.9.2.8.3 AE tables), the following total will be provided in addition:

- "**Total on-trt BI**", defined as the total over all on-treatment phases involving BI 655130

CTR Appendix 16.1.9.2.8.1 displays will present results for the screening and on-treatment phases.

Additionally to the totals defined above, the following total will be provided in CTR Section 16.1.9.2.8.1 AE tables:

- "**Total**", defined as the total over all study phases (incl. screening and on-treatment).

More details on the technical implementation of these analyses are provided in the ADS Plan of this TSAP.

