## **7. PLANNED ANALYSIS**

The format of the listings and tables will follow the BI guideline "Reporting of clinical trials and project summaries" (001-MCG-159) ([10](#)).

The individual values of all subjects will be listed. Listings will generally be sorted by treatment group, subject number and visit (if visit is applicable in the respective listing). AE listings will be sorted by assigned analysis phase (see [Table 6.1: 1](#) for a definition of analysis phases). The listings will be contained in Appendix 16.2 (SDL) of the CTR.

The following standard descriptive statistical parameters will be displayed in summary tables of continuous variables:

N	number of non-missing observations
Mean	arithmetic mean
SD	standard deviation
Min	minimum
Median	median
Max	maximum

For plasma concentrations as well as for all PK parameters, the following descriptive statistics will additionally be calculated:

CV	arithmetic coefficient of variation
gMean	geometric mean
gCV	geometric coefficient of variation

The data format for descriptive statistics of plasma concentrations will be identical with the data format of the respective concentrations. The descriptive statistics of PK parameters will be calculated using the individual values with the number of decimal places as provided by the evaluation program. Then the individual values as well as the descriptive statistics will be reported with three significant digits in the CTR.

Tabulations of frequencies for categorical data will include all possible categories and will display the number of observations in a category as well as the percentage (%) relative to the respective treatment. Percentages will be rounded to one decimal place. The category missing will be displayed if and only if there actually are missing values. Percentages will be based on all subjects in the respective subject set whether they have non-missing values or not.

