### **7.8.1 Adverse events**

AEs will be coded with the most recent version of MedDRA.

The analyses of AEs will be descriptive in nature. All analyses of AEs will be based on the number of subjects with AEs and not on the number of AEs.

For analysis, multiple AE occurrence data on the eCRF will be collapsed into one event provided that all of the following applies:

- All AE attributes are identical (lower level term, intensity, action taken, therapy required, seriousness, reason for seriousness, relationship, outcome, AESI)
- The occurrences were time-overlapping or time-adjacent (time-adjacency of two occurrences is given if the second occurrence started at most 1 hour after the first occurrence ended)

For further details on summarization of AE data, please refer to "Analysis and Presentation of Adverse Event Data from Clinical Trial" ([7](#)) [001-MCG-156] and "Handling of missing and incomplete AE dates" ([4](#)) [001-MCG-156\_RD-01].

The analysis of AEs will be based on the concept of treatment emergent AEs. That means that all AEs will be assigned to the screening phase or on-treatment phase as defined in [Section 6.1](#).

An overall summary of AEs will be presented. This overall summary will comprise summary statistics for the class of other significant AEs according to ICH E3 and for the class of AESIs.

**CTP:** *The AESI in this trial is hepatic injury, as defined by the following alterations of hepatic laboratory parameters:*

- *an elevation of AST and/or ALT  $\geq 3$ -fold ULN combined with an elevation of total bilirubin  $\geq 2$ -fold ULN measured in the same blood sample, and/or*
- *aminotransferase (ALT, and/or AST) elevations  $\geq 10$  fold ULN*

The investigator had to classify on the eCRF whether an observed AE was an AESI or not.

According to ICH E3 ([9](#)), AEs classified as "other significant" need to be reported and will include those non-serious and non-significant AEs

- (i) which are marked haematological or other lab abnormalities, or
- (ii) which were reported with "action taken = discontinuation" or "action taken = reduced", or
- (iii) which lead to significant concomitant therapy as identified by the Clinical Monitor/Investigator at a Medical Quality Review Meeting.

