The frequency of subjects with AEs will be summarised by treatment, primary SOC and preferred term. AEs which were considered by the investigator to be drug related will be summarised separately. Separate tables will also be provided for subjects with SAEs, subjects with AESIs and subjects with other significant AEs (according to ICH E3 ([9](#))). The frequency of subjects with AEs and the frequency of subjects with AEs considered by the investigator to be drug related will also be summarised by maximum intensity, primary SOC and preferred term.

The SOCs and preferred terms within SOCs will be sorted by descending frequency overall treatment groups.

For disclosure of AE data on ClinicalTrials.gov, the frequency of subjects with non-serious AEs occurring with an incidence of greater than 5 % (in preferred terms) will be summarised by treatment, primary SOC and preferred term. The frequency of subjects with SAEs will also be summarised.

For disclosure of AE data in the EudraCT register, the frequency of AEs, the frequency of non-serious AEs with an incidence of greater than 5 % (in preferred terms) and the frequency of SAEs will be summarised.

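### The adverse-event window may run longer for subjects still above LOQ at Day 176, and the SAP compares crude AE percentages with no common cut-off or time at risk

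*Protocol*

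**What the plan says.** The Flow Chart schedules EOT, with a PK sample, at Day 176 ±3. Footnote 15, attached to that sample, adds: "In case plasma levels still exceed LOQ additional PK samples may be collected beyond Day 176 ±3". It gives no rule for who is extended, how many samples are taken or when they stop. Footnote 12 requires "EOT to be performed not before last PK and ADA sampling".

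On adverse events, protocol Section 5.2.2.2 sets the collection period: "From signing the informed consent onwards until an individual subject's end of trial". Because the residual effect period is unknown, the same section states that "all AEs reported until the end of trial examination will be considered on treatment".

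SAP Table 6.1:1 closes the on-treatment phase at "0:00 AM on day after subject's trial termination date". This date is specific to each subject and has no upper limit. For the summaries, SAP Section 7.8.1 says "All analyses of AEs will be based on the number of subjects with AEs and not on the number of AEs" and "The frequency of subjects with AEs will be summarised by treatment, primary SOC and preferred term". SAP Section 7 fixes the denominator: "Percentages will be based on all subjects in the respective subject set whether they have non-missing values or not". SAP Section 5.4.2 defines exposure as total dose, adding infusion duration for the IV group. Time at risk is not summarised anywhere.

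**The concern.** Taken together, these rules let the length of AE observation depend on how much drug is left at Day 176. A subject who is followed longer has at least as high a chance of being counted once as a subject with an AE, whether or not the drug causes any events. Residual level depends on dose and possibly on route, so the groups could end up with different follow-up. A table by treatment would then mix a follow-up difference with a drug difference, in the direction of more events where drug persists.

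Safety and tolerability are a stated objective, and protocol Section 7.3.3 says treatments will be compared descriptively. With 12 subjects per group, one additional subject moves a percentage by 1/12 = 8.3 points. The reader of the report would have no follow-up summary with which to judge whether a difference reflects longer observation.

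**Working it through.** The plan contains no calculation of AE follow-up to reproduce. Its only planning calculation, protocol Table 7.5:1, concerns PK precision and is not at issue. It does reproduce: exp(2w), with w = t(0.95, 22) × √ln(1+gCV²) × √(2/12) × √(χ²(0.95, 22)/22), gives 1.310, 1.246 and 1.133, against the printed 1.31, 1.25 and 1.13.

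**Step 1. Could levels exceed LOQ at Day 176?**
- Inputs from protocol Section 1.2.5: half-life 20.4 to 33.9 days, and geometric mean Cmax of 6.63 to 235 µg/mL in first-in-human dose groups #6 to #10. Day 176 is 4200 h, or 175 days after dosing.
- Formula, assuming mono-exponential decay from Cmax: C = Cmax × 2^(−175/t½).
- Lowest case: 6.63 × 2^(−175/20.4) = 0.017 µg/mL. Highest case: 235 × 2^(−175/33.9) = 6.6 µg/mL.
- For comparison, a group geometric mean Cmax of 0.0228 µg/mL was reported in the same trial.

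Extension is therefore realistic. The decay model overstates late levels, because it ignores distribution and target-mediated loss. The LOQ is not given and the doses are redacted, so the share of subjects above LOQ in each group cannot be derived.

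**Step 2. Extra chance of being counted for one extended subject.**
- Assume a constant AE hazard. Let p be the proportion with an AE by Day 176 and e the extra days. Excess = (1−p) − (1−p)^((176+e)/176).
- Values of p: 62.1% (first-in-human, active arm, protocol Section 1.2.5), 84.4% (all subjects in the multiple-dose trial, same section) and 30% as an assumed low case. The two trial figures are not Day 176 proportions and serve only as illustrations. The range of e, 14 to 84 days, is also assumed.
- Example: p = 62.1%, e = 28. 0.379 − 0.379^(204/176) = 0.379 − 0.325 = 0.054.

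| p by Day 176 | e = 14 | e = 28 | e = 56 | e = 84 |
|---|---|---|---|---|
| 30% | +2.0 | +3.9 | +7.5 | +11.0 |
| 62.1% | +2.8 | +5.4 | +10.1 | +14.0 |
| 84.4% | +2.1 | +4.0 | +7.0 | +9.2 |

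(percentage points)

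**Step 3. Shift between two groups.** For a common extension length, shift = excess × (share extended in group A − share extended in group B).
- All against none, p = 62.1%, 28 days: 5.4 points, or 0.65 of 12 subjects.
- Half against none: 0.5 × 5.4 = 2.7 points.
- Equal shares: 0.

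**Step 4. Scale.** The standard error of a difference between two groups of 12 is √(2p(1−p)/12).
- 62.1%: √(2 × 0.621 × 0.379/12) = 19.8 points.
- 30%: √(2 × 0.3 × 0.7/12) = 18.7 points.
- 84.4%: √(2 × 0.844 × 0.156/12) = 14.8 points.

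Every entry in the table is below the standard error for its row.

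**Step 5. With a common cut-off.** If AEs are counted only to Day 176 + 3 = Day 179 in every subject, events during later sampling no longer enter the comparison, and the shift from that source is 0.

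**The case against.** The strongest reply is that nothing forces the windows apart. Footnote 15 is permissive, and the Flow Chart gives every subject an EOT at Day 176 ±3. Extension could also be decided for a whole group or the whole trial, since footnote 4 already lets sampling times be adapted during conduct. The decay figures above suggest that many subjects in every group might exceed LOQ, in which case the trigger would hardly separate the groups. All of this stands, and it is why the effect is only conditional. It does not remove the problem, because no rule secures equal extension.

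Footnote 12 might be read as fixing only the order of procedures at one visit. Even so, a PK sample taken later would have to precede EOT, so EOT would still move. If EOT did stay at Day 176 ±3, footnote 12 would be breached.

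It is also fair to say that no decision hangs on these tables. Safety is descriptive, no test is planned, AE onset is recorded and individual data are listed, so late events can be found. That limits the harm, but it leaves the summary comparison unadjusted and follow-up time unreported.

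Finally, counting all AEs to EOT is deliberate, because the residual effect period is unknown. This stands, and it is a reason to keep the full tables and add to them.

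**Conclusion.** The point holds as a conditional weakness of the AE analysis. The documents allow a subject-specific AE window that may lengthen with persistent drug level, and the SAP has neither a common cut-off nor a time-at-risk measure. If extension differs between groups, the longer-followed group's percentage can be inflated. Under the assumed constant hazard, with one whole group extended by 14 to 84 days and the other not at all, the inflation is about 2 to 14 points. Partial differences in extension scale this down, and equal extension gives zero. All of these values are below the sampling error with 12 per group.

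A reader might infer more, namely that AE frequency must rise with exposure by the design itself. The documents do not support that. Extension is optional and has no stated length, the SAP tabulates by treatment group and not by measured concentration, and the IV-to-SC exposure relation is what the trial sets out to estimate. A reader might also infer that each two-fold dose step adds one half-life of follow-up. That would require sampling every subject until the level reaches LOQ, which no section says.

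**What to change.** In SAP Sections 6.1 and 7.8.1:
- Keep the full on-treatment AE tables up to each subject's end of trial.
- Add an analysis phase that ends on the same planned day for all subjects, for example the end of the EOT window (Day 179), and base the between-treatment AE comparison on it.
- Show AEs recorded later, during level-driven sampling, in a separate extended follow-up display.
- Report follow-up time by treatment group.

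Protocol Section 7.3.3 already allows further treatment intervals and leaves their definition to the SAP, so the added phase fits the protocol. The Flow Chart EOT row and footnotes 12 and 15 must also be reconciled, so that it is clear whether an optional late sample moves EOT. Holding EOT at Day 176 with PK-only visits afterwards is not proposed as the remedy. Under protocol Section 5.2.2.2, active AE monitoring is no longer required after the individual end of trial, so it would lapse in subjects with measurable drug.

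The cost is one extra analysis phase and its displays. Late AEs would sit outside the common-cut-off comparison but would remain in the full tables and the separate display.
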